10.7 Appendix 7: Country-specific Requirements

Not applicable to this study.

10.8 Appendix 8: Risk Evaluation

At each treatment and follow-up visit as specified in the SoA (Section 1.3.1 and Section 1.3.2), participants will be screened by appropriate study-site personnel for changes in HIV risk behaviors. The following questions should be used based on the CDC Recommended Indications for PrEP [Centers for Disease Control and Prevention 2018]:

- Are you sexually active?
 - If no, no further questions.
 - If yes, are you in a mutually monogamous partnership with a recently tested/known to be HIV-negative partner?
 - If yes, no further questions.
 - If no, is one or more of the following true?
 1. You are in an ongoing sexual relationship with an HIV-positive partner.
 2. You infrequently use condoms during sex with 1 or more partners of unknown HIV status who are known to be at substantial risk of HIV infection (defined as a person who injects drugs, a man who has sex with men, someone sexually active with other partners where the HIV incidence is >3% as per WHO guidelines for PrEP) [World Health Organization 2015].
 3. You have had anal sex without condoms (receptive or insertive) since last visit.
 4. You have had a bacterial STI (syphilis, gonorrhea in women or men) diagnosed or reported since last visit.

Any response of ‘YES’ to the above questions 1 through 4 should be considered a change in HIV risk status and consultation with the Sponsor is required prior to dispensing further study intervention.

Changes in HIV risk status may be discovered by the interviewer-administered questions above, participant’s self-reporting or as deemed by the study investigator or designee upon medical history and/or physical exam review.

Increases in a participant’s HIV risk status at any time during the study should be brought to the attention of the Sponsor. No further study intervention should be administered from the time the site is made aware of the change in risk status until the Sponsor has provided guidance.

Upon assessment of the increase in risk status, the Sponsor will determine: a) the appropriateness of continuing study intervention and/or b) the necessity to refer the participant for applicable services (eg, substance use, mental health, PrEP).

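### The second gate in Appendix 8 asks about the present partnership and can end the risk interview before condomless anal sex since the last evaluation is asked about

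*Protocol*

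**What the plan says.** Section 8.3.6 and the note in the Schedule of Activities (Section 1.3.1) make Appendix 8 (Section 10.8) the tool for changes in HIV risk after Day 1. The appendix states the purpose: "participants will be screened by appropriate study-site personnel for changes in HIV risk behaviors".

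The list has two gates and four items.

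- The first gate asks whether the participant is sexually active; after a no, "If no, no further questions".
- The second gate: "If yes, are you in a mutually monogamous partnership with a recently tested/known to be HIV-negative partner". After a yes, "If yes, no further questions".
- Only a no at the second gate leads to the items. Item 3 is "You have had anal sex without condoms (receptive or insertive) since last visit" and item 4 is "You have had a bacterial STI (syphilis, gonorrhea in women or men) diagnosed or reported since last visit". Items 1 and 2 are in the present tense (item 1: "You are in an ongoing sexual relationship with an HIV-positive partner").

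A yes to any item counts as a change in risk status and requires consultation with the Sponsor before more study intervention is dispensed. Appendix 8 adds that a change may also come to light through self-report or the investigator's review of history or examination. Section 8.3.6 stops dosing once the site learns of a change, until the Sponsor gives guidance.

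**The concern.** The second gate asks about now, while item 3 behind it asks about an interval. The gate can therefore close off the question it stands in front of: a partnership that qualifies today says nothing about a different partner two or three weeks ago.

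What is at stake is the consultation. Under Sections 7.1 and 8.3.6 it leads to the decision to continue study intervention or to refer the participant to prevention services, including approved PrEP. Study drug should not be assumed to cover the gap: about 50 of the 350 participants receive placebo, Section 4.3 projects the 3 mg dose to be suboptimal, and Section 2.3 describes direct individual benefit as minimal. If item 3 is not asked, the consultation depends on the participant volunteering the exposure or the investigator finding it.

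**Working it through.** The plan gives no figure to reproduce here. The check is a trace of the branching, a search for another question that would catch the same exposure, and a comparison of time frames.

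**1. Branch trace.** Take a participant who had condomless anal sex with partner A after the last risk evaluation, and by the next one is mutually monogamous with partner B, who has recently tested HIV-negative.

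- First gate, sexually active: yes, go on.
- Second gate, currently in such a partnership: yes, truthfully. The interview ends.
- Item 3: true of this participant, but not asked. Item 4 is skipped in the same way.

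**2. Other scheduled questions after Day 1.**

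- Medical history is scheduled only at Screening and Day 1 (Section 1.3.1).
- The contraception check covers the interval, but only in participants of childbearing potential and only for contraception (Section 8.3.7).
- STI testing after screening is for symptoms, at the investigator's discretion (Section 8.3.4.2).
- The HIV-1/2 screen is done at every visit with a risk evaluation, but it tests for infection, not exposure.
- A diagnosed STI (item 4) can also appear through adverse event reporting or concomitant medication review. For condomless anal sex I found no other scheduled question.

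**3. Time between risk evaluations.** Evaluations after Day 1 fall at Weeks 4, 8, 12, 16 and 20 and at Follow-up Weeks 4 and 8, nominally 28 days apart. With the dosing windows in Table 4 (Section 8.1.8.1) and no missed visit:

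| Evaluation | Shortest gap (days) | Longest gap (days) |
|---|---|---|
| Week 4 | 27 − 1 = 26 | 31 − 1 = 30 |
| Week 8 | 50 − 31 = 19 | 64 − 27 = 37 |
| Week 12 | 78 − 64 = 14 | 92 − 50 = 42 |
| Week 16 | 106 − 92 = 14 | 120 − 78 = 42 |
| Week 20 | 134 − 120 = 14 | 148 − 106 = 42 |

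A change of partner within one gap is possible.

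**4. Last visit is not the same as last risk evaluation.** Items 3 and 4 look back to the last visit. Day 2 and Follow-up Day 1 (all participants), and Weeks 1 to 3 and Follow-up Week 6 (PBMC Subset), have no risk evaluation. For most participants this costs about a day. In the PBMC Subset (about 20 × 4 = 80 participants) it costs more, at nominal timing:

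- At Week 4 (Day 29) the last visit is Week 3 (Day 22). The look-back is 29 − 22 = 7 days of the 28 since Day 1, leaving 28 − 7 = 21 days uncovered.
- At Follow-up Week 8 the last visit is Follow-up Week 6. The look-back is 14 days of 28, leaving 14 uncovered.

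Rewording the second gate to refer to the last visit would carry this second gap over. The anchor has to be the last risk evaluation.

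**The case against.** **The case is narrow.** The list is repeated about every four weeks. If the earlier partner was already current at the previous evaluation and was untested or not monogamous, the four items were asked then. If that partner was monogamous and HIV-negative, the risk was low. What remains is mainly an exposure that began and ended within one interval, followed by a new qualifying partnership before the visit. This stands, and it is why the point is minor.

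**Present status suits the purpose.** The Schedule of Activities links the list to PrEP eligibility, and current partnership is a reasonable guide to future need. Appendix 8 bases its questions on a cited PrEP guideline; whether the gate follows that source cannot be checked from these documents. This has some force, but items 3 and 4 look back over an interval and the stated purpose is to find changes in behaviour. The gate cuts across both.

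**There are other prompts.** Risk-reduction counselling (Section 8.1.12), the condom offer to sexually active participants and the symptom-directed examination at dosing visits all invite disclosure, and Section 8.3.6 then applies whatever the route. This also stands: the exposure goes unasked, not necessarily undetected. None of these prompts puts the question itself.

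**An interviewer may read the gate as covering the interval.** Some may, but the written rule is to stop, and leaving it to judgement lets practice differ between sites.

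**Conclusion.** The point holds as a cheap improvement to participant protection. Read as written, the second gate lets one relevant exposure go unasked at evaluations from Week 4 onward, and the questionnaire then does not trigger the consultation before dispensing. Day 1 dosing is not affected, because inclusion criterion 2 is used there. The conclusion rests on a literal reading of the gate and its stop instruction. The documents give no exposure rate, so the number affected is unknown; it is probably small.

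A reader might infer more than the documents support in four ways.

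- *That entry is screened more strictly for this behaviour.* Inclusion criterion 2 looks back 12 months, but it does not list condomless anal sex and allows up to 3 partners. It is not a stricter benchmark here.
- *That the number of interviews gives the size.* Five dosing visits × 350 participants = 1,750 counts every dosing interview at full attendance, including those where item 3 is asked. It does not measure affected participants or missed exposures.
- *That the rest of the list fails equally.* The first gate has the same form, but being sexually active can be read as covering recent weeks. The firm case is the second gate with item 3.
- *That trial results are at risk.* The adverse event and PK analyses are unaffected.

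**What to change.** In Appendix 8:

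- Reword the second gate as: *Since your last HIV risk evaluation, has your only sexual partner been a mutually monogamous partner who is recently tested/known to be HIV-negative?* Asking about the only partner means that time without a partner does not count as a no.
- In items 3 and 4, replace the reference to the last visit with *since your last HIV risk evaluation*.
- Optionally, for consistency, give the first gate the same time frame.

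Leave the consultation trigger and the dosing rules as they are.

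The cost is a wording amendment, with the regulatory and ethics review that Section 10.1.1 requires for any amendment. Some participants will answer a few more questions, and there will be occasional additional Sponsor consultations. No visit, procedure or blood draw is added.

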1.3 Schedule of Activities

1.3.1 Schedule of Activities (Main)

Study Period	Screening	Study Intervention (Blinded)											Follow-up (Blinded) ^f				Notes
		1	2	3	4	5	6	7	8	9	10	11	12	13	14	15	
Visit Number	Screening	Day 1	Day 2	Week 1 ^a	Week 2 ^a	Week 3 ^a	Week 4	Week 8	Week 12	Week 16	Week 20/ EOT ^b	Follow-up Day 1 ^c	Follow-up Week 4 ^c (Week 24)	Follow-up Week 6 ^c (Week 26)	Follow-up Week 8 ^c (Week 28)		
Scheduled Day/Week																	
Window	≤45 days	N/A	N/A	±2 days			±7 days			N/A	±7 days	±2 days	±7 days				
Administrative Procedures																	
Informed consent	X																Informed consent marks the start of the screening window.
Informed consent for FBR	X																
Inclusion/exclusion criteria	X	X															Participants may be rescreened 1 time; see Section 8.11.1.2.
Participant identification card	X	X															Add randomization number on Day 1.
Register study visit in IRT	X	X					X	X	X	X	X						
Randomization		X															
Dispense study intervention using IRT and administer study intervention		X					X	X	X	X	X						Directly observed dosing. Add randomization number and visit number to the bottles at time of dispensing.
Offer condoms and lubricant		X					X	X	X	X	X		X				For sexually active participants. Document in participant chart.
Safety Procedures																	
Medical history	X	X															

Study Period	Screening	Study Intervention (Blinded)											Follow-up (Blinded) ^f				Notes
		1	2	3	4	5	6	7	8	9	10	11	12	13	14	15	
Visit Number																	
Scheduled Day/Week	Screening	Day 1	Day 2	Week 1 ^a	Week 2 ^a	Week 3 ^a	Week 4	Week 8	Week 12	Week 16	Week 20/ EOT ^b	Follow-up Day 1 ^c	Follow-up Week 4 ^c (Week 24)	Follow-up Week 6 ^c (Week 26)	Follow-up Week 8 ^c (Week 28)		
Window	≤45 days	N/A	N/A	±2 days			±7 days			N/A	±7 days	±2 days	±7 days				
HIV infection risk evaluation	X	X					X	X	X	X	X		X		X	Document in participant chart. Assess as per Inclusion Criterion #2 at Screening and Day 1 (prior to dose). After Day 1, assess changes in risk status and PrEP eligibility using Appendix 8.	
Prior/concomitant medication review	X	X	X	X	X	X	X	X	X	X	X	X	X	X	X		
Contraceptive use confirmation (POCBP only)	X	X					X	X	X	X	X		X		X	Document in participant chart.	
Complete physical exam	X																
Symptom-directed physical exam		X	X				X	X	X	X	X		X		X		
Vital signs	X	X	X				X	X	X	X	X		X		X	Includes body temperature, pulse, respiratory rate, and systolic and diastolic blood pressure.	

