1.3.2 Schedule of Activities (HIV Infection Confirmation or Early Withdrawal From Study)

Study Period	HIV Infection Confirmation ^a	Early Withdrawal From Study ^b	Notes
Visit Number	Unscheduled		
Scheduled Day/Week	HIV Infection Confirmation	Early Withdrawal From Study	
Visit Window	Within 14 days of HIV-positive test	NA	
Administrative Procedures			
Offer condoms and lubricant	X		For sexually active participants. Document in participant chart.
Register study visit in IRT		X	
Safety Procedures			
HIV infection risk evaluation	X	X	Document in participant chart. Assess any changes in risk status and PrEP eligibility (Appendix 8).
Concomitant medication review	X	X	
Contraceptive use confirmation (POCBP only)	X	X	Document in participant chart.
Symptom-directed physical exam		X	
Vital signs		X	Includes body temperature, pulse, respiratory rate, and systolic and diastolic blood pressure
Weight		X	
AE assessment	X	X	
12-lead ECG		X	Only perform at the Early Withdrawal visit if the participant discontinues prior to the Week 20 ECG collection.
Laboratory Evaluations/Procedures			
HIV-1 and HIV-2 screen		X	
HIV-1 RNA PCR	X		
HIV-1 drug resistance testing	X		
Urine pregnancy test (POCBP only)		X	Conduct per local regulations. Positive results to be confirmed with serum pregnancy test.
Hematology	X	X	
TBNK Panel/CD4+ T-cell count	X	X	
Chemistry		X	
Creatinine clearance calculation (CG)		X	
Cystatin-C		X	
Pharmacokinetics (All participants)			
Plasma PK sample collection	X	X	Not required if participant is beyond Follow-up Day 1.

Study Period	HIV Infection Confirmation ^a	Early Withdrawal From Study ^b	Notes
Visit Number	Unscheduled		
Scheduled Day/Week	HIV Infection Confirmation	Early Withdrawal From Study	
Visit Window	Within 14 days of HIV-positive test	NA	
Pharmacokinetics (PBMC Subset)			Participants are from preselected sites. Refer to laboratory/study operation manual for special collection and processing requirements.
PBMC collection	X	X	
Venous microsampling (eg, Mitra [®] /VAMS)	X	X	

AE=adverse event; CG=Cockcroft-Gault; ECG=electrocardiogram; HIV=human immunodeficiency virus; IRT=Interactive Response Technology; PBMC=peripheral blood mononuclear cells; PCR=polymerase chain reaction; PK=pharmacokinetic; POCBP=participants of childbearing potential; PrEP=pre-exposure prophylaxis; RNA=ribonucleic acid; TBNK=T- and B-lymphocyte natural killer cell; VAMS=volumetric absorptive microsampling.

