5.1 Inclusion Criteria

An individual is eligible for inclusion in the study if the individual meets all of the following criteria:

Type of Participant and Disease Characteristics

1. Is confirmed HIV-uninfected based on negative HIV-1/HIV-2 test result before randomization (completed by the central laboratory).
Note: Additional testing to confirm suspected HIV infection during screening will be performed in accordance with local guidelines. If HIV infection is confirmed, the participant is not eligible for the study and will be referred for appropriate care, as necessary.
2. Has low-risk of HIV infection, defined as all of the following within 12 months prior to the screening visit or the rescreening visit (if applicable) (based on self-report by participant or medical history [if available]):
 - No anal or vaginal intercourse with someone known to be HIV-infected or of unknown HIV infection status who is at increased risk of HIV infection (see Appendix 8);
 - No stimulant use (cocaine [including crack], methamphetamine, or non-physician prescribed pharmaceutical-grade stimulants) or inhaled nitrate;
 - No illicit injection drug use of any kind;
 - No new diagnosis of an STI such as GC, CT, incident syphilis, or trichomoniasis;
 - Not greater than 3 different sexual partners for receptive or insertive vaginal or anal sex; and,
 - No history of antiretrovirals for HIV-1 PrEP or PEP.

Note: Individuals who have participated in studies of an antiretroviral, such as Phase 1 studies (excluding MK-8527 and MK-8591), may be eligible after consultation with the Sponsor.

Demographics

3. Is an individual of any sex/gender, from 18 years to 65 years of age inclusive, at the time of providing the informed consent.

Male Participants

Note: Contraceptive use by male participants should be consistent with local regulations regarding the methods of contraception for those participating in clinical studies.

Female Participants

4. A participant assigned female sex at birth is eligible to participate if not pregnant or breastfeeding, and at least one of the following conditions applies:
 - Is not a POCBP
OR
 - Is a POCBP and:

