8.3.6 HIV Risk Evaluation

At screening and again at Day 1 prior to randomization, a participant's risk status should be evaluated based on Inclusion Criterion #2 (Section 5.1). A participant that does not meet all elements of Inclusion Criterion #2 should not be randomized. After randomization (Day 1), at each treatment and follow-up visit as specified in the SoA (Sections 1.3.1 and 1.3.2), participants will be screened by appropriate study-site personnel for changes in HIV risk behaviors based on the list of questions included in Appendix 8.

Any participant who develops a risk for HIV infection at any time during the study should be brought to the attention of the Sponsor. No further study intervention should be administered from the time the site is made aware of the change in risk status until the Sponsor has provided guidance.

Upon assessment of the increase in risk status, the Sponsor will determine: a) the appropriateness of continuing study intervention and/or b) the necessity to refer the participant for applicable services (eg, substance use, mental health, PrEP).

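### After Day 1 the scripted HIV risk screen never asks whether the participant injects drugs, although injecting bars entry

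*Protocol*

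**What the plan says.** Criterion 2 in Protocol 5.1 defines low HIV risk over the 12 months before screening or rescreening. One of its required elements is "No illicit injection drug use of any kind". It is applied at Screening and Day 1.

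The tool then changes. The main Schedule of Activities (1.3.1) says: "After Day 1, assess changes in risk status and PrEP eligibility using Appendix 8". Section 8.3.6 agrees: "participants will be screened by appropriate study-site personnel for changes in HIV risk behaviors based on the list of questions included in Appendix 8". For the HIV Infection Confirmation and Early Withdrawal visits, Section 1.3.2 also points sites to Appendix 8.

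Appendix 8 opens by asking about sexual activity, with the instruction "If no, no further questions". A second question lets out participants who are mutually monogamous with an HIV-negative partner. Everyone else gets four items: an HIV-positive partner, infrequent condom use with at-risk partners, anal sex without condoms, and a bacterial STI. Injecting is mentioned once, in item 2, about partners: "partners of unknown HIV status who are known to be at substantial risk of HIV infection (defined as a person who injects drugs". A yes to any of the four requires Sponsor consultation before further dosing.

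There is also a general provision in Section 8.3.6: "Any participant who develops a risk for HIV infection at any time during the study should be brought to the attention of the Sponsor". Dosing then stops "from the time the site is made aware of the change in risk status until the Sponsor has provided guidance". Appendix 8 accepts self-report and investigator judgement as ways of finding a change, and substance-use services are among the referrals named.

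**The concern.** The protocol treats injecting as disqualifying at entry, regards a partner who injects as being at substantial HIV risk, and provides for substance-use referral. Yet the prescribed question list for the rest of the study does not ask the participant about it. A partner's injecting can contribute to a trigger; the participant's own cannot. No reason is given for the difference.

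At stake is the start of Sponsor review, and with it referral for PrEP or substance-use services. Section 7.1 also relies on Appendix 8 when a change in risk behaviour may lead to discontinuation or to approved PrEP, so the omission reaches that decision too. No arm is established PrEP: one is placebo, and Section 4.3 projects 3 mg to be suboptimal. A missed referral therefore matters in all four arms.

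**Working it through.** The documents state no figure to reproduce. The check compares the two tools and counts the visits.

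**1. Content.** Each element of Criterion 2 (Protocol 5.1) against the Appendix 8 script:

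| Criterion 2 element | Asked in Appendix 8? |
|---|---|
| Sex with a partner who has HIV, or of unknown status and at increased risk | Largely, items 1 and 2 |
| Stimulants or inhaled nitrate | No |
| Participant's own illicit injecting | No; injecting describes a partner only |
| New STI | Item 4, bacterial only, after two exits |
| More than 3 sexual partners | No |
| Prior antiretrovirals for PrEP or PEP | No |

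The script has 2 opening questions + 4 items = 6 questions. Of these, 0 concern the participant's own injecting.

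**2. Branches.** A participant who is not sexually active is asked 1 question. A monogamous participant with an HIV-negative partner is asked 2. Only the remainder reach items 1 to 4. Injecting risk does not depend on sexual activity, so adding an item after the exits would still miss the first two groups.

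**3. Visits (Schedule of Activities, 1.3.1, HIV risk evaluation row).**
- Criterion 2: Screening, Day 1 = 2.
- Appendix 8: Weeks 4, 8, 12, 16, 20 and Follow-up Weeks 4 and 8 = 7.
- Total for a completer: 2 + 7 = 9.
- Appendix 8 visits with dosing: Weeks 4, 8, 12, 16, 20 = 5.
- Span: Day 1 to Follow-up Week 8 (Week 28) = 28 weeks.

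**4. Other routes to detection after Day 1.**
- Medical history is scheduled only at Screening and Day 1, and later physical examinations are symptom-directed (1.3.1).
- Concomitant medication review (8.1.5.2) records medication and is not written to ask about illicit injecting.
- Adverse event enquiry is to be open-ended and non-leading (8.4.2).
- Hepatitis B and C testing is at Screening only.
- HIV testing takes place at all 7 visits, but it detects infection, not the risk before it.

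None of these supplies a scheduled prompt about injecting.

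**The case against.** The strongest reply is that the pathway exists and only a prompt is missing. Section 8.3.6 covers any emerging HIV risk, and Appendix 8 admits self-report and investigator judgement. Two further routes deserve mention. Section 10.3.3 gives drug dependency or abuse as an example of an important medical event usually considered serious, and serious events reach the Sponsor within 24 hours. Section 8.1.12 offers HIV risk-reduction counselling. Few participants are likely to be affected, given Criterion 2 and Exclusion 4, which lets the investigator exclude for drug use. A scripted question still depends on an honest answer, and nothing shows how many more cases it would find.

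Much of this is fair, and it limits the weight of the point. It does not close the gap. The serious-event route needs the event to surface under non-leading questioning and may not capture isolated injecting. The content of the counselling is not specified. Every route, including the hold, depends on the site becoming aware, which is what the missing question would help with.

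The reach also differs by visit. At the two follow-up visits, and at an Early Withdrawal visit after the Week 20 dose, no further dose is due and only referral is at issue. At HIV Infection Confirmation, a positive screen has already started confirmatory testing.

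**Conclusion.** The concern holds. None of the 6 scripted questions, at any of the 7 scheduled evaluations after Day 1, asks about the participant's own injecting. The two unscheduled visit types have the same omission. A participant who starts injecting can pass the script truthfully, and Sponsor review and referral may not begin.

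The textual gap is certain. Its practical size is not: the documents give no rate of new injecting, and the entry exclusion suggests it is low. The conclusion assumes that sites follow the script as written and add no question of their own. The primary safety analysis and the SAP's power tables are unaffected. This is a worthwhile, inexpensive correction for participant protection, not a threat to the study's conclusions.

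**What to change.** In Appendix 8, ahead of the opening question on sexual activity, ask every participant whether they have injected any illicit drug since the last visit. Treat a yes as a change in HIV risk status requiring Sponsor consultation before further dosing, as for items 1 to 4. Because the schedules already refer to Appendix 8, the change carries through to the scheduled and unscheduled visits.

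The direct cost is one question, assumed to take about a minute or less, at 7 visits where the screen is already done. The indirect cost is the dosing hold after a yes. From Table 4, a participant seen on the ideal day leaves the Sponsor 31 − 29 = 2 days to respond at Week 4. At Week 8 it is 64 − 57 = 7 days, and the ±7-day window gives the same at Weeks 12, 16 and 20. A later answer would normally cost 1 of the 6 doses, most plausibly at Week 4. Section 8.1.8.1 lets the skipped-dose rule be modified in consultation with the Sponsor, which limits that cost.
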